This patient and observer blinded prospective randomized study will be performed on patients (aged 10 - 17years, both males and females, from all ethnic backgrounds) undergoing multilevel thoraco-lumbar spine surgery with instrumentation and fusion at Texas Children's Hospital, Houston, TX. After obtaining IRB (Institutional Review Board) approval and written informed consent from each patient or his or her legal representative, 56 patients scheduled for multilevel thoraco-lumbar spine surgery with instrumentation and fusion will randomly be assigned into two groups (control or treatment group) based on a computer generated random number using Random Allocation Software For Parallel Group Randomized Trials. There is an equal chance of being assigned to either group. The control group will be given placebo; whereas the treatment group will receive methadone 0.2 mg/kg intravenously.

Inclusion Criteria:

- 1) Patient age 10 \geq 17 years
- 2) Patients undergoing multilevel thoraco-lumbar spine surgery with instrumentation and fusion

Exclusion Criteria:

- 1) Preoperative methadone therapy
- 2) Inability to use the PCA
- 3) Allergy to methadone or morphine
- 4) Morbid obesity with a body mass index >36.0 kg/m²
- 5) Patients with chronic renal failure defined by serum creatinine >2.0 mg/dL
- 6) Liver failure defined as a history of cirrhosis or fulminant hepatic failure
- 7) Preoperative congenital heart disease or arrhythmias
- 8) Patient refusal to participate in study
- 9) Pregnancy (It is standard of care for all post menarche female patients to undergo a urine pregnancy test prior to surgery).

F2. Procedure

The perioperative management of patients will be in keeping with the current standard practices at Texas Children's Hospital. Before surgery, patients will be asked to rate their baseline pain using a verbal rating scale from 1 to 10 by a member of the research team. In addition, information on preoperative opioid consumption during the last 30 days will be collected.

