Postoperative Analgesia All groups: In keeping with current practice, supplemental oxygen will be available for oxygen saturations less than 94% during spontaneous ventilation. All patients will be monitored with continuous pulse oximetry as in keeping with practice at TCH. Every patient will have a patient controlled analgesia (PCA) morphine pump with a basal rate infusion of 0.01 mg/kg/hour, a demand dose 0.02 mg/kg with a lockout time of 10 minutes to be started in the PACU once the patient emerges from the anesthetic. The patient will be administered diazepam 0.05 mg/kg IV or oral with maximum of 5 mg every 6 hours as needed for muscle spasms in keeping with current practice. On POD 1, the basal rate of morphine will be discontinued and ketorolac 0.5 mg/kg every 6 hours initiated in keeping with current practices. On POD 3, the patient will be transitioned from the PCA with scheduled oral hydrocodone/acetaminophen at a dosage of 0.135 mg/kg of hydrocodone with a maximum of 15 mg every 4 hours in keeping with current practice. The PCA will be available for use during the transition for breakthrough pain.

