Postoperatively, patients will be asked to rate their pain using a validated pain scale (a verbal rating scale where 0 = no pain and 10 = worse pain ever) by a blinded research staff member. These pain scores will be collected at 1 hour after entry into recovery and every 4 hours during the first five days of hospitalization both at rest and during activity by the nurses. The cumulative intravenous opioid requirement at 24, 48, and 72 hour will be recorded. The cumulative breakthrough intravenous opioid requirement after initiation of oral pain medication will also be collected. The level of sedation will be determined using the University of Michigan Sedation Scale. In addition, complications such as the incidence of hypotension (defined as mean arterial blood pressure less than 50 mm Hg), the need for vasopressors, the incidence of respiratory depression (defined as a respiratory rate less than 8 breaths per minute, respiratory arrest, or the need for naloxone), the incidence of hypoxemia or desaturation (defined as oxygen saturation [Sao₂] less than 90% or the need for a supplemental oxygen to maintain Sao₂ greater than 94%), the incidence of cardiac arrhythmias, and the incidence of nausea and vomiting including the treatment of side effects will be also recorded. Upon discharge from the hospital, the patients will be asked to keep a diary consisting of daily opioid usage, episodes of nausea and vomiting, daily activity level, and satisfaction scores. As part of standard routine post-surgical followup in the orthopedic clinic, information is collected from the patients which consist of questionnaires regarding pain scores, functional status, activity level, and quality of life. The research team will collect this information at 3 months and 6 months postoperatively.

Section G: Sample Size/Data Analysis**G1. Sample Size**

How many subjects (or specimens, or charts) will be used in this study?

Local: 98

Worldwide: 98

Please indicate why you chose the sample size proposed:

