The sample size was based on the assumption that opioid use in the first 3 days in the placebo group would be similar to that in a previously published study of the same patient population undergoing spine surgery (mean 275 mg SD 75 mg). A group size of 28 would be required for an 80% power of detecting a 30% reduction in opioid use from 275 to 200 mg at the 0.05 level of significance. Allowing for a 50% dropout rate for incomplete data, we will recruit 49 patients in each group for a total of 98 subjects.

G2. Data Analysis

Provide a description of your plan for data analysis. State the types of comparisons you plan (e.g. comparison of means, comparison of proportions, regressions, analysis of variance). Which is the PRIMARY comparison/analysis? How will the analyses proposed relate to the primary purposes of your study?

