The primary endpoint of the study is the morphine consumption during the first 72 postoperative hours. The secondary outcomes include pain scores and the incidence of side effects such as respiratory depression, nausea, and vomiting. Continuous data including pain scores will be first examined for a normal distribution by the Shapiro χ Wilk test. The outcome variables between the two groups will be compared with Student's t -test where appropriate, for normally distributed continuous data or by nonparametric tests if the data were not normally distributed. It is anticipated that the distribution of pain scores will not be normal and that non-parametric tests will be required. Categorical data including patient gender, ASA physical status, incidence of side effects (respiratory depression, need for oxygen beyond the first 2 hours, nausea and vomiting) will be compared by Fisher's exact test. Analysis of variance for repeated measures will be performed to compare differences in pain scores between the treatment groups with time. Data will be presented as mean, standard deviation, median values or numbers (percentages). P values less than 0.05 will be considered statistically significant. In order to maintain a robust statistical analysis, we will also examine the differences in subjects with and without completely evaluable data in known factors that affect postoperative pain after spine surgery (e.g., age, gender, ASA physical status, duration of surgery, intraoperative opioids medications, time of the PACU stay, mean and peak pain scores and recorded opioid consumption in the PACU before discharge). Failure to show a difference in these factors may suggest that the missing data can be considered to be missing at random.

Section H: Potential Risks/Discomforts

H1. Potential Risks/Discomforts

Describe and assess any potential risks/discomforts; (physical, psychological, social, legal, or other) and assess the likelihood and seriousness of such risks:

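### Optional gain: the primary comparison uses no baseline covariate; if consumption is analysed in mg and rises with body weight, prespecifying weight would narrow the confidence interval

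*Combined protocol and SAP*

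**What the plan says.** G2 makes morphine consumption over the first 72 postoperative hours the primary endpoint. On method it says "The outcome variables between the two groups will be compared with Student's t -test where appropriate", or "by nonparametric tests if the data were not normally distributed". It does not name the nonparametric test. No covariate enters the comparison. The patient factors listed later in G2 serve only to compare subjects with and without complete data, and weight is not among them. The allocation described in F1 mentions no stratification.

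Neither F2 nor G2 gives a unit for consumption. The only unit is in the sample-size assumption in G1, "mean 275 mg SD 75 mg", which is absolute mg.

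F2 sets the PCA per kg: "a basal rate infusion of 0.01 mg/kg/hour, a demand dose 0.02 mg/kg with a lockout time of 10 minutes". It then states "On POD 1, the basal rate of morphine will be discontinued". F2 also says "The cumulative intravenous opioid requirement at 24, 48, and 72 hour will be recorded". F1 enrols patients aged 10 to 17 and excludes "Morbid obesity with a body mass index" above a limit. Weight is therefore needed both for dosing and for eligibility, and should be known for every patient before treatment.

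**The concern.** When each dose scales with body weight and patients range from 10 to 17 years, some of the between-patient spread in mg may simply be spread in weight. A t-test on mg leaves that spread in the error term. A linear model with treatment and weight removes it at the cost of one degree of freedom.

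What is at stake is the width of the interval around the treatment effect, and power if the true reduction is smaller than planned. Evaluable numbers are also uncertain: G1 says "Allowing for a 50% dropout rate for incomplete data, we will recruit 49 patients in each group". Half of 49 is 24.5, so between about 24 and 49 per group may be analysed.

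**Working it through.** **Inputs.** From G1: control mean 275 mg, SD 75 mg, planned difference 275 − 200 = 75 mg, 28 per group, 49 recruited per group, level 0.05 (two-sided assumed). Assumed, because the documents give neither a weight SD nor a correlation: r, the within-group correlation of weight with mg, from 0 to 0.7. Also chosen for this check: a smaller true effect of 15%, 0.15 × 275 = 41.25 mg.

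**The plan's own figure.** For 75 mg with SD 75 mg, 80% power needs 17 per group by the t-test, not 28. At 28 per group the power is 95.7%. The mismatch is a separate matter. Here it means that power for the planned effect is already high.

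**Unadjusted half-width** = t(0.975, 2n−2) × 75 × √(2/n). At n = 28: 2.005 × 75 × √(2/28) = 2.005 × 20.04 = 40.2 mg.

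**Adjusted half-width** = t(0.975, 2n−3) × 75 × √(1−r²) × √(2/n) × √(1 + 1/(2n−4)). The last factor is the average cost of chance imbalance in weight. At n = 28, r = 0.5: 2.006 × 20.04 × 0.866 × √(1 + 1/52) = 35.2 mg.

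| 95% CI half-width, mg | Unadjusted | r = 0 | 0.1 | 0.2 | 0.3 | 0.5 | 0.7 |
|---|---|---|---|---|---|---|---|
| 24 per group | 43.6 | 44.1 | 43.9 | 43.2 | 42.1 | 38.2 | 31.5 |
| 28 per group | 40.2 | 40.6 | 40.4 | 39.8 | 38.7 | 35.2 | 29.0 |
| 49 per group | 30.1 | 30.2 | 30.1 | 29.6 | 28.8 | 26.2 | 21.6 |

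Break-even r is 0.15, 0.14 and 0.10 at 24, 28 and 49 per group. At 28 per group and r = 0.5 the interval is 12.5% narrower. Simulation at 28 per group (8,000 trials per value of r, normal data) gave adjusted-to-unadjusted width ratios of 1.010, 0.964, 0.875 and 0.722 at r = 0, 0.3, 0.5 and 0.7, with coverage of about 95%.

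**Power** (noncentral t, 28 per group):

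| True difference | Unadjusted | r = 0 | 0.2 | 0.3 | 0.5 | 0.7 |
|---|---|---|---|---|---|---|
| 75 mg (planned) | 95.7% | 95.3% | 96.0% | 96.8% | 98.7% | 99.9% |
| 41.25 mg | 52.4% | 51.7% | 53.3% | 55.5% | 63.7% | 80.0% |

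**The whole pathway, rank route kept.** G2 switches test on the Shapiro-Wilk result, so the gain arises only when the t-test would be used. Simulated with 28 per group, 10,000 trials per cell, an additive shift of 41.25 mg, and Shapiro-Wilk in each group at 0.05 (assumed; G2 gives neither the level nor the grouping). The revised pathway uses the weight model with HC2 robust standard errors in place of the t-test:

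| Data shape | Shapiro-Wilk passed | r = 0 | r = 0.3 | r = 0.5 |
|---|---|---|---|---|
| Normal | 90% | 51.4 → 50.8% | 51.7 → 54.7% | 52.7 → 62.5% |
| Lognormal, CV 0.27 (r on log scale) | 51% | 55.7 → 55.4% | 55.3 → 56.9% | 55.8 → 61.6% |
| Shifted lognormal, log-SD 0.8 | 0.3% | about 90%, both | about 90%, both | about 90%, both |

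Type I error was 4.4–5.4% for the planned pathway and 4.4–5.6% for the revised one.

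**Is a useful r plausible?** If mg were weight times an independent mg/kg requirement, r would equal CV(weight)/CV(mg). With CV(mg) = 75/275 = 0.27, assumed weight CVs of 0.10 and 0.20 give r = 0.37 and 0.73. The real link is probably weaker because demands are patient-triggered. The basal infusion is a small share: 0.01 × 24 h × 40 kg = 9.6 mg, or × 70 kg = 16.8 mg (weights and duration assumed), which is 3.5% and 6.1% of 275 mg. Scheduled hydrocodone starts only on POD 3, so it matters mainly if the POD 0–4 total opioid endpoint of Section D applies.

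**The case against.** The strongest reply is that nothing is wrong. An unadjusted t-test is valid under randomization, and the benefit depends on three things the documents do not establish: analysis in mg, r above about 0.14, and data that pass Shapiro-Wilk. For the effect the trial was sized on, power rises by at most about 3 points up to r = 0.5 at 28 per group, and it is already 99.8% unadjusted at 49. The 41 mg effect is not the plan's. A proportional 15% reduction on lognormal data (CV 0.27, assumed weight CV 0.20, 4,000 trials) gave only 61% to 62% at r = 0.3 and 60% to 66% at r = 0.5. The revised analysis would also use weight or not according to a pretest, when one could argue for fitting the weight model unconditionally.

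These facts stand, and they limit the size of the gain. They do not remove it, because a narrower interval is useful even when power is ample and the cost is close to nil. On the pretest, using the weight model in every case has its own price: at r = 0 its power was 52% against 55% for the Wilcoxon test under mild skew, and 59% against 90% under heavy skew. Keeping the rank route avoids that trade-off but leaves the plan's data-driven choice of test in place.

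**Conclusion.** The point holds as an optional efficiency gain; the planned test is valid. If the outcome is in mg and the t-test route is taken, adjusting for weight at 28 per group narrows the interval by about 4% at r = 0.3, 12.5% at r = 0.5 and 28% at r = 0.7. The gain is negligible at r = 0.2, and the interval is about 1% wider at r = 0. The correlation is unknown, so the size of the gain is a range and confidence in it is moderate. Under heavy skew the change has no effect, because the rank test is nearly always used.

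**What to change.** In G2, before unblinding, specify that:

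1. consumption is analysed in mg;
2. where the t-test would apply, the treatment difference in mg is estimated from a linear model with treatment and baseline body weight, with HC2 robust standard errors and a 95% confidence interval;
3. the nonparametric route stays, with its test named (for example Wilcoxon rank-sum).

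If the team prefers mg/kg as the outcome, this change is not needed. Dividing by weight already takes much of the gain when r is high but loses power when r is low. Under an assumed mean weight of 55 kg with CV 0.20, a t-test on mg/kg has 36%, 48%, 60% and 79% power for the 41 mg effect at r = 0, 0.3, 0.5 and 0.7, against 52%, 56%, 64% and 80% for weight-adjusted mg.

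The cost is wording only, with no new data. If weight proves unrelated to consumption, the loss is one degree of freedom, an interval about 1% wider and under 1 point of power; over the whole pathway the simulated loss at r = 0 was 0.6 points (normal), 0.3 (mild skew) and 0.0 (heavy skew). Two matters are outside this fix: whether to keep the Shapiro-Wilk selection, and reconciling the POD 0–4 endpoint in Section D with the 72-hour endpoint in G2.

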The aim of this study is to explore the efficacy of a single intra-operative dose of methadone in patients with idiopathic scoliosis undergoing multi-level posterior instrumentation and spinal fusion. The primary endpoints is the total opioid usage during POD (postoperative day) 0-4. Secondary endpoints include and pain scores during rest and with activity (getting out bed and ambulation) on POD 0-5 and side effects of pain medications

Section E: Protocol Risks/Subjects

E1. Risk Category

Category 2: Research involving greater than minimal risk, but presenting the prospect of direct benefit to the individual subjects.

E2. Subjects

Gender:
Both

Age:

Adolescent (13-17 yrs), Child (3-12 yrs)

Ethnicity:

All Ethnicities

Primary Language:

English, Spanish

Groups to be recruited will include:

Patients

Which if any of the following vulnerable populations will be recruited as subjects?

Children

Vulnerable populations require special protections. How will you obtain informed consent, protect subject confidentiality, and prevent undue coercion?

Patients presenting for spinal surgery will be identified from the Texas Children's Hospital operating room schedule that is routinely available to pediatric anesthesiologists. This will be cross referenced with the pediatric orthopedic surgeons' operative schedule as these cases are scheduled weeks to months in advance. The chart is reviewed to insure that the patient qualifies based on the inclusion and exclusion criteria.

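### Pain over time is compared by repeated-measures ANOVA, with no rule that keeps a patient whose in-hospital scores stop before the window ends

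*Combined protocol and SAP*

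**What the plan says.** All references are to the combined protocol and SAP.

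- **Over-time analysis (Section G2).** "Analysis of variance for repeated measures will be performed to compare differences in pain scores between the treatment groups with time". The form of the model, the times that enter and the handling of a patient with some scores missing are not stated.
- **Other pain analysis (Section G2).** Pain scores are also checked for normality (Shapiro-Wilk) and compared by t-test or a nonparametric test, the latter being expected. How scores are grouped for these tests, and which pain analysis leads, is not stated.
- **Missing data (Section G2).** "we will also examine the differences in subjects with and without completely evaluable data in known factors". Then: "Failure to show a difference in these factors may suggest that the missing data can be considered to be missing at random". No imputation, mixed model, available-data rule or sensitivity analysis follows.
- **Window and schedule.** Section D sets "pain scores during rest and with activity (getting out bed and ambulation) on POD 0-5". Section F2 has a score one hour after arrival in recovery, then "every 4 hours during the first five days of hospitalization both at rest and during activity".
- **After discharge (Section F2).** "Upon discharge from the hospital, the patients will be asked to keep a diary consisting of daily opioid usage, episodes of nausea and vomiting"; the remaining diary items are activity and satisfaction. Clinic questionnaires at 3 and 6 months do cover pain.
- **Timing of recovery (Section F2).** "On POD 3, the patient will be transitioned from the PCA with scheduled oral hydrocodone/acetaminophen". No length of stay is given.

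**The concern.** Classical repeated-measures ANOVA needs a full row of times for each patient. A patient who goes home on POD 3 or 4 has no scores for the last days of the window. Neither the diary nor the later clinic questionnaires can supply them. In that form of the analysis the patient's earlier scores are discarded too.

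If early discharge has nothing to do with pain, this costs precision only. If patients with less pain leave sooner, and methadone reduces pain, the methadone arm loses more of its low-pain patients and the estimated benefit shrinks.

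The missing-data text does not close the gap. It is a diagnostic and keeps no one in the analysis. The factors it lists as examples stop at the PACU, so as listed they cannot show whether ward pain drives discharge. A null comparison does not establish missing at random. Even if missing at random held, a complete-patient ANOVA would not in general be unbiased when missingness depends on earlier pain. A likelihood-based model can use that assumption, but the plan names none.

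**Working it through.** The plan has no figure for missing pain scores, so there is none to reproduce. I use 49 per group, 98 in all, from Section G1. (Section F1 speaks of 56 patients; with that number the counts scale by 56/98 = 0.57.) All rates, SDs, correlations and effects below are assumptions.

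1. **Scoring times.** Every 4 hours for five days: 5 × 24/4 = 30 per condition, or 31 with the one-hour score.

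2. **Scattered gaps.** With a chance m that any one value is missing, independently, and T values entered, expected complete patients = 98 × (1 − m)^T.
   - T = 31: m = 1%, 2%, 5% gives 71.8, 52.4, 20.0.
   - T = 6 (one value per day): 92.3, 86.8, 72.0.
   - T = 31 with gaps clustered within patients (beta-binomial, ICC 0.1): 85.3, 74.2, 48.6.

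3. **Early discharge.** If a share q leaves before POD 5, complete patients = 98 × (1 − q): 98 × 0.8 = 78.4 and 98 × 0.7 = 68.6.

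4. **Discharge unrelated to pain.** There is no bias. Relative to full data, interval width grows by 1/√(1 − q): 1/√0.8 = 1.12 and 1/√0.7 = 1.20. Simulated ratios against a likelihood model are 1.11–1.12 and 1.17–1.19.

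5. **Discharge related to pain.** Simulation, 3,000 runs per setting: 49 per group; six daily means (control 6, 5.5, 5, 4.5, 4, 3.5); SD 2; AR(1) day-to-day correlation ρ; methadone 1.0 point lower every day. Discharge at the end of POD 3 or POD 4 follows a logistic model on that day's pain, calibrated to 20% or 30% leaving before POD 5. Complete-patient estimates of the true 1.0:

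| Log-odds of discharge per point lower pain | 20% leave, ρ = 0.5 / 0.7 / 0.9 | 30% leave, ρ = 0.5 / 0.7 / 0.9 |
|---|---|---|
| 0 | 0.99–1.00 | 0.99–1.00 |
| 0.5 | 0.94 / 0.92 / 0.89 | 0.92 / 0.89 / 0.85 |
| 1.0 | 0.88 / 0.83 / 0.77 | 0.84 / 0.78 / 0.71 |

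   The likelihood estimate (unstructured covariance) is 0.99 throughout. Repeat runs gave 0.71–0.96 for complete patients under pain-related discharge and 0.99–1.02 for likelihood.

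6. **Power at ρ = 0.7, 30% leaving.** Complete-patient power is 77%, 72% and 67% for log-odds 0, 0.5 and 1.0, against about 90% for likelihood. Hand check: the variance of a six-day mean is (4/36) × [6 + 2 × (5×0.7 + 4×0.49 + 3×0.343 + 2×0.2401 + 0.1681)] = 2.25, SD 1.50. With 49 per group the SE is 1.50 × √(2/49) = 0.303 and power Φ(1/0.303 − 1.96) = Φ(1.34) = 91%. With 34.3 per group the SE is 0.362 and power Φ(0.80) = 79%, close to the simulated 77%.

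7. **Limits of the illustration.** The likelihood result is partly built in, because discharge was generated from observed pain. When discharge depends on the next day's unobserved pain, likelihood gives 0.93–1.00. Daily differences on all available patients, averaged over days, give 0.91–1.00; these stand in for the plan's two-group tests if run by day.

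**The case against.** The best case for the plan has four parts.

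- **A second pain analysis exists.** Section G2 also plans t-tests or nonparametric tests of pain. Run by time or by day, they may keep every observed patient, and step 7 shows little distortion there. This stands. A reader might infer that the trial's pain result as a whole would be biased downward; the documents do not support that, because the problem touches one of two planned pain analyses.
- **Early discharge is not stated.** The schedule and the POD 0–5 window read as if most patients are expected to stay, and the PCA remains available during the POD 3 transition. This also stands. Discharge inside the window is plausible but is an inference.
- **The form of ANOVA is not stated.** Software may fit repeated measures as a mixed model, which would keep partial data. True, but the plan does not say so, and the choice should not wait until the data are seen.
- **The bias is modest and conservative.** At log-odds 0.5 it is 0.06 to 0.15 points on a 0–10 scale, toward no effect, on a secondary outcome. This limits the weight of the point but does not remove it.

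Two other strong readings fail. The 50% allowance in Section G1 belongs to the opioid endpoint's sample size, so it does not show that half the pain data will be missing. Nor do the documents show inflated false positives. The uncorrected group-by-time test rejects 9–18% of the time under the null only if all four-hourly times enter without a sphericity correction. On daily means it is 5.3–8.4%, and the between-group main effect stays near 5%.

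**Conclusion.** The point holds as a cheap improvement to a secondary analysis. Section G2 names a method that in its classical form discards partly observed patients, for a series collected only in hospital, and nothing in the plan keeps those patients in.

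The size rests wholly on assumed length of stay, missing rate, SD, correlation and effect. At 20–30% leaving before POD 5, the cost runs from lost precision alone to an estimate of about 0.7–0.95 where the truth is 1.0. If nearly all patients stay through the window and daily means are used, the loss is small. The primary opioid comparison is not affected.

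**What to change.** Replace the repeated-measures ANOVA sentence in Section G2 with:

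> Pain scores will be averaged per patient per postoperative day, separately for rest and activity, using all available scores. Days with no score are left missing, and every patient with at least one scored day is kept. Each condition will be analysed by a linear mixed model (REML) with treatment, day, treatment-by-day and baseline pain, and an unstructured covariance by day (a simpler structure if it does not converge). The treatment difference averaged over days, the treatment-by-day test and daily differences with 95% confidence intervals will be reported, with the number of patients contributing per day by group.

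In the same edit:

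- State that this model is the main pain analysis and that the Shapiro-Wilk, t-test and nonparametric comparisons by day are supportive. Otherwise the section holds two pain analyses with no order.
- Add a simple sensitivity analysis for scores missing after discharge, for example shifting the unobserved scores over a stated range.
- Reconcile the scales in Section F2: at baseline "patients will be asked to rate their baseline pain using a verbal rating scale from 1 to 10", but postoperatively the scale starts at 0.
- Reconcile POD 0–5 in Section D with the five-day schedule in Section F2.

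The cost is SAP wording and standard software, with no new data and no change in sample size. The downsides are these. The model assumes missing at random and roughly normal daily means, although the plan expects non-normal raw scores. POD 0 and the discharge day are partial days. Daily averaging loses within-day detail.

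### G2's repeated-measures ANOVA of pain leaves open the effect read, the scores entered and the sphericity correction; on one permitted reading its group-by-time test has about 8–17% error, if serial correlation is 0.5–0.85

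*Combined protocol and SAP*

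**What the plan says.** All references are to the combined protocol and SAP. Section F2 (Procedure) sets the schedule: "These pain scores will be collected at 1 hour after entry into recovery and every 4 hours during the first five days" of the hospital stay, "both at rest and during activity by the nurses". Section D (Purpose and Objectives) gives a slightly different window, postoperative days 0 to 5.

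Section G2 (Data Analysis) makes pain secondary: "The secondary outcomes include pain scores and the incidence of side effects such as respiratory depression, nausea, and vomiting". Three statements there bear on how pain is compared:

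- General rule: "The outcome variables between the two groups will be compared with Student's t -test where appropriate, for normally distributed continuous data", with nonparametric tests otherwise.
- Expectation for pain: "It is anticipated that the distribution of pain scores will not be normal and that non-parametric tests will be required".
- Longitudinal analysis: "Analysis of variance for repeated measures will be performed to compare differences in pain scores between the treatment groups with time".

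The threshold is "P values less than 0.05 will be considered statistically significant". G2 names no effect to be read from the ANOVA, no set of time points, no covariance structure, no sphericity test or correction, and no confidence interval for the difference in pain.

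**The concern.** Pain scored every 4 hours is likely to be serially correlated: neighbouring scores resemble each other more than scores days apart. The classical within-patient F-test assumes sphericity, which such a pattern breaks, and the test then rejects too often unless its degrees of freedom are reduced.

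The ANOVA sentence refers to differences between groups over time, which can be read as the group-by-time term. That is the term exposed to the inflation. It also asks only whether the gap between arms changes, not whether there is a gap.

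The paragraph further expects rank tests for pain and then prescribes a normal-theory method, with no rule for which one answers the question. The choice of term, time points and method could therefore be made after the data are seen. Section I says the data can show whether methadone gives better pain control, so a spurious finding, or a missed steady difference, would matter to readers even though pain is secondary.

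**Working it through.** **Inputs from the documents.** Scores per series: 1 + (5 × 24)/4 = 31, in two series (F2). Group sizes: 28 evaluable or 49 recruited per arm (G1). Nominal level 0.05 (G2). The documents give no error rate or power for the pain ANOVA, so there is no plan figure to reproduce.

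**Assumption.** No within-patient correlation is given. Serial correlation was taken as AR(1), with adjacent-score correlation varied from 0 to 0.95.

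**Test.** With p = 31 times and n per arm, the uncorrected group-by-time F has p − 1 = 30 and 30(2n − 2) degrees of freedom: 30 × 54 = 1,620 at n = 28, and 30 × 96 = 2,880 at n = 49. The departure from sphericity is ε = tr(M)² / [(p − 1) tr(M²)], where M is the covariance matrix after each patient's mean is removed. Greenhouse-Geisser multiplies both degrees of freedom by an estimate of ε. A patient random effect cancels from M, so only the serial part matters.

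**Rejection rates with no true effect** (4,000 runs per cell, Monte Carlo SE about 0.3–0.6 points; paired figures are 28 / 49 per arm):

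| Serial correlation | ε | Group-by-time, uncorrected | Group-by-time, Greenhouse-Geisser | Group main effect |
|---|---|---|---|---|
| 0 | 1.00 | 6.0% / 4.6% | 2.6% / 2.8% | 4.8% / 5.3% |
| 0.3 | 0.845 | 6.1% / 6.8% | 2.5% / 3.6% | 4.6% / 5.1% |
| 0.5 | 0.622 | 9.3% / 8.7% | 3.6% / 3.6% | 5.0% / 4.8% |
| 0.7 | 0.375 | 13.3% / 12.8% | 3.8% / 4.6% | 5.0% / 5.0% |
| 0.8 | 0.261 | 15.6% / 15.6% | 4.6% / 4.5% | 5.7% / 4.3% |
| 0.9 | 0.160 | 18.0% / 16.4% | 4.4% / 4.4% | 4.8% / 4.7% |
| 0.95 | 0.118 | 19.3% / 19.5% | 5.3% / 5.0% | 4.7% / 4.5% |

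**Sensitivity checks.**

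- Compound symmetry (correlation 0.5, n = 28): 4.8% uncorrected.
- Patient effect taking 40% of the variance (n = 28): 9.1%, 12.9% and 18.2% at 0.5, 0.7 and 0.9.
- Scores rounded and clipped to 0–10 (n = 28): 8.3%, 13.0% and 18.5% at the same correlations. Non-normality of this kind is therefore not what drives the inflation.
- Rounded scores plus a patient effect of 30–50% of variance (1,500 runs): 8–10%, 12–13% and 15–17% at 0.5, 0.7 and 0.85, and 4–7% at 0–0.3.
- Five or six daily values (n = 28, correlation 0.5–0.9 between successive values): 6.2–9.3%.

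**Constant difference.** The interaction uses d(t) = [ȳ₁(t) − ȳ₁] − [ȳ₂(t) − ȳ₂], where ȳ₁ and ȳ₂ are the arm means over all times. Adding a constant to every score in one arm leaves d(t) unchanged. In simulation with a constant 0.5 SD shift, 28 per arm and correlation 0.5, 0.7 and 0.9, uncorrected group-by-time rejects 9.0%, 12.7% and 18.8%, which is its null rate within simulation error. The group main effect rejects 100%, 99.4% and 79.0%.

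With a patient effect of 30–50% of variance, SD 2.2, a constant 1-point reduction and correlation 0.5–0.7, the time-averaged difference has 60–76% power at 28 per arm and 81–96% at 49. Corrected group-by-time rejects 2–5%.

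**The case against.** The strongest reply is that G2 under-specifies rather than errs. It answers a form that asks for types of comparison, and silence on a correction is not a decision to omit one. Four parts of this reply stand.

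- **The term read.** G2 never says that group-by-time is the test. The same ANOVA gives a group main effect that holds about 5% error without correction, and a two-group test is also planned. A reader might infer that the plan cannot detect a steady difference in pain; the documents do not support that.
- **The correlation.** High correlation between scores is not enough to cause the problem. With a patient effect of 30–50% of variance and serial correlation 0.3, total adjacent correlation is 0.3 + 0.7 × 0.3 = 0.51 to 0.5 + 0.5 × 0.3 = 0.65, yet error stays near nominal. A reader might take 8–17% as this trial's error rate; it is conditional on an assumption.
- **The scores entered.** Thirty-one is the collection schedule. G2 does not say that all of them enter the ANOVA.
- **Separate tests at each time.** A reader might infer 31 rank tests with the multiplicity that follows. G2 does not propose them.

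It is also fair that G2 plans means, SDs and medians, so only an interval for the difference is missing. After a single dose, a changing difference is a legitimate question.

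What the reply does not meet is that G2 is the analysis description given, and it leaves the term, the time points and the correction to be settled later. The two-group test does not fill the gap, because no summary score or time point is named for it.

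**Conclusion.** The point holds as a conditional one. G2 does not fix the effect, the time points or the covariance treatment for pain, and its ANOVA sits unreconciled beside an expectation of non-normal scores and rank tests. If all 31 scores enter, group-by-time is read and no correction is made, error is about 8–17% for serial correlation 0.5–0.85 beyond the patient effect. Across every setting tried it runs from about 5% to 19–20%. A Greenhouse-Geisser correction brings it back to about 5% or below. Blindness to a constant difference belongs to the group-by-time term alone.

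The change should be made, but it concerns a secondary outcome and leaves the primary opioid comparison and the sample size untouched. The inflation is nearly the same at 28 and 49 per arm, so the conclusion does not depend on which group size is reached.

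**What to change.** Replace the ANOVA sentence in G2 with one named comparison for rest and one for activity: the between-group difference in time-averaged pain over a single stated window, with a 95% CI. State the window, since sections D and F2 differ, and state which scores enter. Obtain the estimate from a mixed model with group, time, group-by-time and a serial covariance, or by comparing patients' mean scores between arms. Say that this comparison is the answer for pain, and what role, if any, a rank test keeps.

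Report group-by-time as supportive, with a Greenhouse-Geisser or model-based p-value.

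The cost is one paragraph and a little analysis work, with no new data. The downside is that an average over several days can dilute or hide an early difference, so daily means by arm should be shown beside it.
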